4.2.3 Rationale for Endpoints

4.2.3.1 Safety Endpoints

The primary safety objective of this trial is to characterize the safety and tolerability of MK-3475 administered in a neoadjuvant setting in patients with RCC. The primary safety analysis will be based on subjects who experienced toxicities as defined by CTCAE criteria. Safety will be assessed by quantifying the toxicities and grades, including serious adverse events (SAEs) and events of clinical interest (ECIs), experienced by all subjects who have received MK-3475.

Safety will be assessed by reported adverse experiences using CTCAE, Version 4.0. The attribution to drug, time-of-onset, duration of the event, its resolution, and any concomitant medications administered will be recorded. AEs to be analyzed will include but will not be limited to all AEs, SAEs, fatal AEs, and laboratory changes. Furthermore, potential immune-related adverse events (irAEs) will be collected and designated as immune-related events of clinical interest (ECIs) as described in Section 7.2.3.2.

Because all patients with RCC treated with neoadjuvant MK-3475 in this trial will undergo subsequent SOC operative tumor resection, surgical complications will be assessed. The following information related to surgery will be recorded: blood transfusions in the perioperative period, length of hospital stay, readmission, and surgical complications including the need for surgical re-exploration, thromboembolic events, cardiovascular events, pulmonary complications, gastrointestinal complications, postoperative infection, and incision-related complications.

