5.2.1.2 Dose Modification and Toxicity Management Guidelines for Pembrolizumab

Dose modification and toxicity management for immune-related AEs associated with pembrolizumab

AEs associated with pembrolizumab exposure may represent an immunologic etiology. These immune-related AEs (irAEs) may occur shortly after the first dose or several months after the last dose of pembrolizumab treatment and may affect more than one body system simultaneously. Therefore, early recognition and initiation of treatment is critical to reduce complications. Based on existing clinical trial data, most irAEs were reversible and could be managed with interruptions of pembrolizumab, administration of corticosteroids and/or other supportive care. For suspected irAEs, ensure adequate evaluation to confirm etiology or exclude other causes. Additional procedures or tests such as bronchoscopy, endoscopy, skin biopsy may be included as part of the evaluation. Based on the severity of irAEs, withhold or permanently discontinue pembrolizumab and administer corticosteroids. Dose modification and toxicity management guidelines for irAEs associated with pembrolizumab are provided in [Table 6](#) for neoadjuvant dosing and [Table 3](#) for post-resection dosing.

5.2.1.2.1.1 Neoadjuvant MK-3475

Based on the first interim analysis of lymphocytic infiltrates in tumors resected from the first 9 subjects, if an increase in tumor lymphocytic infiltration of 2-fold or greater is not observed in more than one of the 6 subjects in this group that received a 2 dose course of neoadjuvant

MK-3475, all subsequent subjects enrolled in this trial may be treated with 3 doses of MK-3475. Details are described in Section 8.0 – Statistical Analysis Plan.

Administration of neoadjuvant MK-3475 during this trial must be discontinued for drug-related toxicities above Grade 1 in severity and for severe or life-threatening AEs as described in Section 5.6.1. Such subjects should proceed with SOC surgical RCC resection as soon as they have sufficiently recovered from the AE to undergo this procedure.

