| Diarrhea / Colitis | Grade 2 or 3 | Withhold | 
 Administer corticosteroids (initial dose of 1-2 mg/kg prednisone or equivalent) followed by taper | 
 Monitor participants for signs and symptoms of enterocolitis (ie, diarrhea, abdominal pain, blood or mucus in stool with or without fever) and of bowel perforation (ie, peritoneal signs and ileus). Participants with \geq Grade 2 diarrhea suspecting colitis should consider GI consultation and performing endoscopy to rule out colitis. Participants with diarrhea/colitis should be advised to drink liberal quantities of clear fluids. If sufficient oral fluid intake is not feasible, fluid and electrolytes should be substituted via IV infusion. |
| | Grade 4 | Permanently discontinue | | |

| Immune-related AEs | Toxicity grade or conditions (CTCAEv4.0) | Action taken to pembrolizumab | irAE management with corticosteroid and/or other therapies | Monitor and follow-up |
|--|--|--|---|---|
| AST / ALT elevation or Increased bilirubin | Grade 2 | Withhold | 
 Administer corticosteroids (initial dose of 0.5- 1 mg/kg prednisone or equivalent) followed by taper | 
 Monitor with liver function tests (consider weekly or more frequently until liver enzyme value returned to baseline or is stable) |
| | Grade 3 or 4 | Permanently discontinue | 
 Administer corticosteroids (initial dose of 1-2 mg/kg prednisone or equivalent) followed by taper | |
| Type 1 diabetes mellitus (T1DM) or Hyperglycemia | Newly onset T1DM or Grade 3 or 4 hyperglycemia associated with evidence of β -cell failure | Withhold | 
 Initiate insulin replacement therapy for participants with T1DM Administer anti-hyperglycemic in participants with hyperglycemia | 
 Monitor participants for hyperglycemia or other signs and symptoms of diabetes. |
| Hypophysitis | Grade 2 | Withhold | 
 Administer corticosteroids and initiate hormonal replacements as clinically indicated. | 
 Monitor for signs and symptoms of hypophysitis (including hypopituitarism and adrenal insufficiency) |
| | Grade 3 or 4 | Withhold or permanently discontinue ¹ | | |

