| Hyperthyroidism | Grade 2 | Continue | 
 Treat with non-selective beta-blockers (eg, propranolol) or thionamides as appropriate | 
 Monitor for signs and symptoms of thyroid disorders. |
| | Grade 3 or 4 | Withhold or permanently discontinue ¹ | | |
| Hypothyroidism | Grade 2-4 | Continue | 
 Initiate thyroid replacement hormones (eg, levothyroxine or liothyronine) per standard of care | 
 Monitor for signs and symptoms of thyroid disorders. |
| Nephritis and Renal dysfunction | Grade 2 | Withhold | 
 Administer corticosteroids (prednisone 1-2 mg/kg or equivalent) followed by taper. | 
 Monitor changes of renal function |
| | Grade 3 or 4 | Permanently discontinue | | |

| Immune-related AEs | Toxicity grade or conditions (CTCAEv4.0) | Action taken to pembrolizumab | irAE management with corticosteroid and/or other therapies | Monitor and follow-up |
|--|---|---|---|--|
| Myocarditis | Grade 1 or 2 | Withhold | 
 Based on severity of AE administer corticosteroids | 
 Ensure adequate evaluation to confirm etiology and/or exclude other causes |
| | Grade 3 or 4 | Permanently discontinue | | |
| All other immune-related AEs | Intolerable/persistent Grade 2 | Withhold | 
 Based on type and severity of AE administer corticosteroids | 
 Ensure adequate evaluation to confirm etiology and/or exclude other causes |
| | Grade 3 | Withhold or discontinue based on the type of event. Events that require discontinuation include and not limited to: Guillain-Barre Syndrome, encephalitis | | |
| | Grade 4 or recurrent Grade 3 | Permanently discontinue | | |
| 
1. Withhold or permanently discontinue pembrolizumab is at the discretion of the investigator or treating physician.
 
NOTE: For participants with Grade 3 or 4 immune-related endocrinopathy where withhold of pembrolizumab is required, pembrolizumab may be resumed when AE resolves to \leq Grade 2 and is controlled with hormonal replacement therapy or achieved metabolic control (in case of T1DM).
 | | | | |

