| Appropriate resuscitation equipment should be available in the room and a physician readily available during the period of drug administration. For Further information, please refer to the Common Terminology Criteria for Adverse Events v4.0 (CTCAE) at http://ctep.cancer.gov | | |

5.6.1.1 Supportive Care Guidelines for Events of Clinical Interest (ECIs) and Immune-Related Adverse Events (irAEs) During Neoadjuvant MK-3475 Only

Events of clinical interest of a potential immunologic etiology may be defined as an adverse event of unknown etiology, associated with drug exposure and is consistent with an immune phenomenon. irAEs may be predicted based on the nature of MK-3475, its mechanism of action, and reported experience with immunotherapies that have a similar mechanism of action. Special attention should be paid to AEs that may be suggestive of potential irAEs. An irAE can occur shortly after the first dose or several months after the last dose of treatment.

If an irAE is suspected, efforts should be made to rule out neoplastic, infectious, metabolic, toxin or other etiologic causes prior to labeling an adverse event as an irAE. Subjects who develop a Grade 2 or higher irAEs should be discussed immediately with the Sponsor.

Recommendations for managing irAEs during the neoadjuvant phase of the trial that are not detailed elsewhere in the protocol are detailed in [Table 6](#).

Table 6 General Approach to Handling irAEs- **Neoadjuvant Phase Only**

| irAE | Discontinue study treatments? | Supportive Care |
|---------------------|--|--|
| Grade 1 | No action | Provide symptomatic treatment. |
| Grade 2 | Discontinue neoadjuvant MK-3475 treatment. | Consider systemic corticosteroids in addition to appropriate symptomatic treatment. |
| Grade 3 and Grade 4 | Discontinue neoadjuvant MK-3475 treatment. | Systemic corticosteroids are indicated in addition to appropriate symptomatic treatment. May utilize 1 to 2 mg/kg prednisone or equivalent per day. Steroid taper should be considered once symptoms improve to Grade 1 or less and tapered over at least 4 weeks. |

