7.2.3.2 Events of Clinical Interest

Selected non-serious and serious adverse events are also known as Events of Clinical Interest (ECI) and must be recorded as such on the Adverse Event case report forms/worksheets and reported within 24 hours to the Sponsor either by electronic media or paper. Sponsor Contact information can be found in the Investigator Trial File Binder (or equivalent).

Events of clinical interest for this trial include:

1. an overdose of Sponsor's product, as defined in Section 7.2.1 - Definition of an Overdose for This Protocol and Reporting of Overdose to the Sponsor, that is not associated with clinical symptoms or abnormal laboratory results.
2. an elevated AST or ALT lab value that is greater than or equal to 3X the upper limit of normal and an elevated total bilirubin lab value that is greater than or equal to 2X the upper limit of normal and, at the same time, an alkaline phosphatase lab value that is less than 2X the upper limit of normal, as determined by way of protocol-specified laboratory testing or unscheduled laboratory testing.*

***Note:** These criteria are based upon available regulatory guidance documents. The purpose of the criteria is to specify a threshold of abnormal hepatic tests that may require an additional evaluation for an underlying etiology. The trial site guidance for assessment and follow up of these criteria can be found in the Investigator Trial File Binder (or equivalent).

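### For Grade 1 myocarditis only, the rules before nephrectomy permit another dose of MK-3475, while the rules after resection withhold it

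*Combined protocol and SAP*

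**What the plan says.** Section 5.2.1.2 divides toxicity management by phase: Table 6 for neoadjuvant dosing, Table 3 for post-resection dosing.

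- **Before surgery.** Table 6 (Section 5.6.1.1) reads "Grade 1 | No action | Provide symptomatic treatment". Section 5.2.1.2.1.1 says that neoadjuvant drug "must be discontinued for drug-related toxicities above Grade 1 in severity". After such a stop, "Such subjects should proceed with SOC surgical RCC resection as soon as they have sufficiently recovered from the AE to undergo this procedure". The explicit rule on talking to the Sponsor also starts one grade up: "Subjects who develop a Grade 2 or higher irAEs should be discussed immediately with the Sponsor".
- **After surgery.** Table 3, whose title limits it to the post-resection phase, has the row "Myocarditis | Grade 1 or 2 | Withhold". It adds corticosteroids according to severity and a work-up of the cause.

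The dose is 200 mg every 3 weeks in both phases.

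**The concern.** Tolerability of neoadjuvant MK-3475 in patients about to have a nephrectomy is a primary objective. For the mildest grade of a cardiac immune-related event, the written dosing rule just before major surgery is less cautious than the rule the sponsor applies after it. No reason is given. The Summary of Changes suggests how the difference arose: the myocarditis guidance came in when the post-resection table was replaced, to match current safety information, and neither Section 5.2.1.2.1.1 nor Section 5.6.1.1 is listed as revised.

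At stake is a rare subject's safety. Sample size, the posterior-probability thresholds and Table 14 are not affected.

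**Working it through.** **1. Does any neoadjuvant rule other than Table 6 cover myocarditis?** The event-specific neoadjuvant rules are enterocolitis (Section 5.6.1), infusion reactions (Table 5) and pneumonitis (Table 7). None names myocarditis. Table 6 is for events not detailed elsewhere in the protocol, and Table 3 does detail myocarditis. But Table 3's title and the split in Section 5.2.1.2 keep it out of the neoadjuvant phase, so myocarditis falls to Table 6.

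**2. Compare the two phases grade by grade for myocarditis.**

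| Grade | Neoadjuvant (Table 6, 5.2.1.2.1.1) | Post-resection (Table 3) | Stricter phase |
|---|---|---|---|
| 1 | Dosing may continue | Withhold | Post-resection |
| 2 | Discontinue | Withhold | Neoadjuvant |
| 3 or 4 | Discontinue | Permanently discontinue | Equal |

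**3. Does the gap extend to other events?** Table 3 has 10 event rows: pneumonitis, diarrhea/colitis, AST/ALT/bilirubin, diabetes/hyperglycemia, hypophysitis, hyperthyroidism, hypothyroidism, nephritis, myocarditis, and all other. Only 1 of the 10, myocarditis, names Grade 1.

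**4. Could Table 3's hold simply be copied into Table 6?** Not usefully. The neoadjuvant course is 2 doses, possibly 3. Section 5.8 requires discontinuation from the trial after more than 7 consecutive days' interruption or one missed dose, and discontinued subjects may not restart treatment. A hold before surgery is therefore in effect a stop, and the text should say so.

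**5. How would a Grade 1 case be found?** Table 11 describes Grade 1 as asymptomatic or mild. The flow charts in Sections 6.1 and 6.3 schedule one ECG, at screening, and after that only if clinically indicated. Table 10 lists no cardiac marker. Detection would be mostly incidental.

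**6. Size.** The chance of at least one event among n subjects at rate p is 1 − (1 − p)^n. Check against Table 13 at p = 1%, n = 33: 1 − 0.99^33 = 28.2%, stated 28%. It reproduces.

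The documents give no myocarditis rate, so the rates below are assumptions. The sample sizes of 24 and 33 neoadjuvant subjects come from Table 4.

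| Assumed rate, any grade | n = 24 | n = 33 |
|---|---|---|
| 0.1% | 2.37% | 3.25% |
| 0.5% | 11.33% | 15.25% |
| 1% | 21.43% | 28.23% |

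These are chances of any case at all. A case that is Grade 1, is recognised, and arises with a neoadjuvant dose still to come is only part of them.

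**The case against.** The best defence is that the scheme is phase-specific on purpose and leaves room for judgement. Section 5.6 warns that supportive-care guidance differs between the phases. Section 5.2.1.2 opens with general text asking for evaluation of suspected events and for withholding or stopping according to severity. The threshold in Section 5.2.1.2.1.1 is a floor for stopping, not a ban on stopping at Grade 1. Section 5.8 lets an investigator withdraw a subject, and Section 5.6.1 points to a binder document on managing these events, which is not available here and may address myocarditis.

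All of that stands as mitigation: the rules permit a further dose, they do not require it. It does not override the specific Grade 1 line in Table 6. Caution also meets some friction: Section 7.1.1.8 requires Sponsor consultation and written documentation for an interruption, and the missed-dose rule in Section 5.8 follows.

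A reader might infer more than the text supports:

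- **That neoadjuvant rules are generally laxer.** They are not. Any drug-related Grade 2 toxicity ends neoadjuvant dosing, while Table 3 continues drug through Grade 2 hyperthyroidism and Grade 2 to 4 hypothyroidism.
- **That a site gets two conflicting instructions.** The tables have separate scopes, so it does not.
- **That new-onset diabetes is a second gap.** Its Table 3 trigger, "Newly onset T1DM or Grade 3 or 4 hyperglycemia associated with evidence of" beta-cell failure, gives no grade for new-onset disease. But Table 3 calls for insulin, and Table 11 defines Grade 1 as needing no intervention, so such a case is not Grade 1.
- **That the Sponsor would never hear of it.** Section 4.2.3.1 says that "potential immune-related adverse events (irAEs) will be collected and designated as immune-related events of clinical interest (ECIs"), with no grade limit. The list in Section 7.2.3.2 that opens "Events of clinical interest for this trial include" names only overdose and a liver-test criterion, so the route is unclear rather than absent.

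**Conclusion.** The point holds in a narrow form: one grade of one event, in 1 of the 10 Table 3 rows. It is a cheap improvement, not a flaw in the design or the analysis. The reading of the text is firm. The practical effect is small, and the number of affected subjects cannot be estimated because no rate is given and few Grade 1 cases would be detected. The conclusion assumes that the binder guidance does not already impose a stop; if it does, the change only brings the protocol into line.

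**What to change.** In the next amendment:

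1. Add a Table 6 row for Grade 1 myocarditis: give no further neoadjuvant MK-3475, evaluate the cause before surgery, and discuss with the Sponsor. This adapts Table 3's hold to a course too short to allow one.
2. Add the matching exception to the above-Grade-1 threshold in Section 5.2.1.2.1.1.
3. State that such a subject proceeds to resection as in that section and is not removed under the missed-dose rule of Section 5.8. Without this, the subject could lose up to 17 post-resection doses, which matters most in metastatic disease.
4. For Grade 1 only, decide post-resection eligibility under Table 3. Leave unchanged the bar in Section 5.2.1.2.1.1 on post-resection drug for subjects without metastases whose neoadjuvant toxicity exceeded Grade 1. Extending the Table 3 route to all grades would loosen that bar, because Table 3 only withholds at Grade 2.

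The cost is one table row and two or three sentences, plus a pre-surgery evaluation for an affected subject. The downside is that a rare subject misses a neoadjuvant dose and may need replacement (Section 5.9) for the per-protocol PD analysis (Section 8.2.3). The change adds no new detection.

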5.6.1.2 Supportive Care Guidelines for Pneumonitis- Neoadjuvant MK-3475 Only

Subjects with symptomatic pneumonitis should immediately stop receiving treatments and have an evaluation. The evaluation may include bronchoscopy and pulmonary function tests to rule out other causes such as infection. For subjects who are determined to have study drug associated pneumonitis, the suggested treatment plan is outlined in [Table 7](#).

Table 7 Recommended Approach for Handling Pneumonitis- Neoadjuvant Phase Only

| Study Drug Associated Pneumonitis | Discontinue study treatments? | Supportive Care |
|-----------------------------------|--|---|
| Grade 1 (asymptomatic) | No action | Intervention not indicated |
| Grade 2, 3 and 4 | Discontinue neoadjuvant MK-3475 treatment. | Systemic corticosteroids are indicated. |

5.6.2 Supportive Care Guidelines During Post-Resection MK-3475 Treatment for this Trial

Subjects should receive appropriate supportive care measures as deemed necessary by the treating investigator. Suggested supportive care measures for the management of AEs with potential immunologic etiology are outlined along with the dose modification guidelines in Section 5.2.1.2, [[Table 3](#)]. Where appropriate, these guidelines include the use of oral or IV treatment with corticosteroids, as well as additional anti-inflammatory agents if symptoms do not improve with administration of corticosteroids. Note that several courses of steroid tapering may be necessary as symptoms may worsen when the steroid dose is decreased. For each disorder, attempts should be made to rule out other causes such as metastatic disease or bacterial or viral infection, which might require additional supportive care. The treatment guidelines are intended to be applied when the Investigator determines the events to be related to pembrolizumab.

Note: If after the evaluation of the event, it is determined not to be related to pembrolizumab, the Investigator does not need to follow the treatment guidance. Refer to [Table 3] in Section 5.2.1.2 for guidelines regarding dose modification and supportive care.

It may be necessary to perform conditional procedures such as bronchoscopy, endoscopy, or skin photography as part of evaluation of the event.

Dose modification and toxicity management of infusion-reactions related to pembrolizumab

Pembrolizumab may cause severe or life threatening infusion-reactions including severe hypersensitivity or anaphylaxis. Signs and symptoms usually develop during or shortly after drug infusion and generally resolve completely within 24 hours of completion of infusion. Dose modification and toxicity management guidelines on pembrolizumab associated infusion reaction are provided in [Table 8](#).

Table 8 Pembrolizumab Infusion Reaction Dose modification and Treatment Guidelines-Post-Resection Phase Only

| NCI CTCAE Grade | Treatment | Premedication at Subsequent Dosing |
|---|---|---|
| Grade 1 Mild reaction; infusion interruption not indicated; intervention not indicated | Increase monitoring of vital signs as medically indicated until the subject is deemed medically stable in the opinion of the investigator. | None |
| Grade 2 Requires therapy or infusion interruption but responds promptly to symptomatic treatment (e.g., antihistamines, NSAIDs, narcotics, IV fluids); prophylactic medications indicated for ≤ 24 hrs | Stop Infusion. Additional appropriate medical therapy may include but is not limited to: IV fluids Antihistamines NSAIDs Acetaminophen Narcotics Increase monitoring of vital signs as medically indicated until the subject is deemed medically stable in the opinion of the investigator. If symptoms resolve within 1 hour of stopping drug infusion, the infusion may be restarted at 50% of the original infusion rate (e.g. from 100 mL/hr to 50 mL/hr). Otherwise dosing will be held until symptoms resolve and the subject should be premedicated for the next scheduled dose. Subjects who develop Grade 2 toxicity despite adequate premedication should be permanently discontinued from further study drug treatment | Subject may be premedicated 1.5h (\pm 30 minutes) prior to infusion of _____ with: Diphenhydramine 50 mg po (or equivalent dose of antihistamine). Acetaminophen 500-1000 mg po (or equivalent dose of analgesic). |

| NCI CTCAE Grade | Treatment | Premedication at Subsequent Dosing |
|--|---|------------------------------------|
| Grades 3 or 4 Grade 3: Prolonged (i.e., not rapidly responsive to symptomatic medication and/or brief interruption of infusion); recurrence of symptoms following initial improvement; hospitalization indicated for other clinical sequelae (e.g., renal impairment, pulmonary infiltrates) Grade 4: Life-threatening; pressor or ventilatory support indicated | Stop Infusion. Additional appropriate medical therapy may include but is not limited to: Epinephrine** IV fluids Antihistamines NSAIDs Acetaminophen Narcotics Oxygen Pressors Corticosteroids Increase monitoring of vital signs as medically indicated until the subject is deemed medically stable in the opinion of the investigator. Hospitalization may be indicated. **In cases of anaphylaxis, epinephrine should be used immediately. Subject is permanently discontinued from further study drug treatment. | No subsequent dosing |

Appropriate resuscitation equipment should be available at the bedside and a physician readily available during the period of drug administration.

For further information, please refer to the Common Terminology Criteria for Adverse Events v4.0 (CTCAE) at <http://ctep.cancer.gov>

Other allowed dose interruption for pembrolizumab

Pembrolizumab may be interrupted for situations other than treatment-related AEs such as medical / surgical events or logistical reasons not related to study therapy. Subjects should be placed back on study therapy within 3 weeks of the scheduled interruption, unless otherwise discussed with the Sponsor. The reason for interruption should be documented in the patient's study record.

